### **3.8.3. Selection of Non-Efficacy Data in the Event of Multiple Records in an Analysis Visit Window**

Depending on the statistical analysis method, single values may be required for each analysis window. For example, change from baseline by visit usually requires a single value, whereas a time-to-event analysis would not require 1 value per analysis window.

If multiple valid, nonmissing, continuous measurements exist in an analysis window, records will be chosen based on the following rules if a single value is needed:

- In general, the baseline value will be the last nonmissing value on or prior to the first dose date of study drug, unless otherwise specified. If multiple measurements occur on the same day, the last nonmissing value prior to the time of first dose of study drug will be considered as the baseline value. If these multiple measurements occur at the same time or the time is

not available, the average of these measurements (for continuous data) will be considered the baseline value.

- For postbaseline visits:
  - The record closest to the nominal day for that visit will be selected.
  - If there are 2 records that are equidistant from the nominal day, the later record will be selected.
  - If there is more than 1 record on the selected day, the average will be taken, unless otherwise specified.

If multiple valid, nonmissing, categorical measurements exist in an analysis window, records will be chosen based on the following rules if a single value is needed:

- For baseline, the last available record on or prior to the date of the first dose of study drug will be selected. If there are multiple records with the same time or no time recorded on the same day, the value with the lowest severity will be selected.
- For postbaseline visits:
  - The record closest to the nominal day for that visit will be selected.
  - If there are 2 records that are equidistant from the nominal day, the later record will be selected.
  - If there is more than 1 record on the selected day, the value with the worst severity will be taken, unless otherwise specified.

The rules for selecting efficacy data in the event of multiple records in an analysis visit window are specified in Section 6.1.

## 4. SUBJECT DISPOSITION

### 4.1. Subject Enrollment and Disposition

A summary of subject enrollment will be provided by treatment group for each country, investigator within a country, and overall. The summary will present the number and percentage of subjects enrolled. For each column, the denominator for the percentage calculation will be the total number of subjects analyzed for that column.

A summary of subject disposition will be provided by treatment group. This summary will present the number of subjects screened, the number of subjects randomized, and the number of subjects in each of the categories listed below:

- Safety Analysis Set
- Full Analysis Set
- Completed study drug
- Did not complete study drug with reasons for premature discontinuation of study drug
- Completed study
- Did not complete study with reasons for premature discontinuation from the study

For the status of study drug and study completion and reasons for premature discontinuation, the number and percentage of subjects in each category will be provided. The denominator for the percentage calculation will be the total number of subjects in the Safety Analysis Set corresponding to that column.

### 4.2. Extent of Study Drug Exposure and Adherence

Extent of exposure to study drug will be examined by assessing the total duration of exposure to study drug.

#### 4.2.1. Duration of Exposure to Study Drug

Total duration of exposure to any study drug will be defined as (last dose date of any study drug - first dose date of any study drug + 1), regardless of any temporary interruptions in study drug administration and will be expressed in weeks using up to 1 decimal place (eg, 4.5 weeks).

If the last study drug dosing date is missing, the latest date among the study drug end date, clinical visit date, laboratory sample collection date, weight and vital signs assessment date that occurred during the on-treatment period will be used.

The total duration of exposure to any study drug will be summarized using descriptive statistics and using the number (ie, cumulative counts) and percentage of subjects exposed through the following time periods: Baseline (Day 1), Week 1 (Day 8), Week 4 (Day 29), Week 8 (Day 57), and Week 12 (Day 85).

Summaries will be provided by treatment group for the Safety Analysis Set. No formal statistical testing is planned.

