3.4. Duration of Treatment

Subjects will receive 12 SC injections of weekly study drug (GS-5745 or placebo) in the blinded period and up to 53 weekly doses of GS-5745 in the OLE.

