5.3. Dosage and Administration of GS-5745 and Placebo to Match

Subcutaneous injections of study drug (GS-5745/PTM) should be administered to 1 of 4 locations: to the right thigh, left thigh, right abdomen, or left abdomen (abdominal injections should be made at or below the level of the navel, avoiding the area within 5 cm [two inches] of the navel). If a subject is dosing their TNF inhibitor medication on the same day as their study drug, the subject should be instructed to inject their TNF inhibitor in a different site than the study drug. Information regarding which site was used for study drug injection will be collected throughout the study.

GS-5745 or placebo will be administered SC at the research center at Day 1 and Weeks 1, 4 and 8 during the blinded part of the study. All injections should be delivered within 1 hour of the first SC injection. The investigator or a qualified designee must be present during the administration of SC injections at Day 1 and Week 1. After training for SC injection at the study site, the subject will be allowed to administer the remaining weekly SC study drug doses at

home, except for those doses which coincide with scheduled study visits; in those cases, the study drug should be administered at the site, under direction of study staff (to enable timing for PK blood draws or other study procedures).

During the OLE portion of the study, GS-5745 will be administered SC at the research center at Weeks 12 and 13. Afterwards, subject will administer the subsequent weekly SC study drug doses at home, except for those doses which coincide with scheduled study visits; in those cases, the study drug should be administered at the site, under direction of study staff (to enable timing for PK blood draws or other study procedures).

In any part of the study, if the subject has a body temperature of $> 38^{\circ}\text{C}$ (100.4°F), or the subject feels unwell or is otherwise unfit to receive study drug at a given scheduled weekly injection, the subject should not be administered study drug. In consultation with the medical monitor, the Investigator may delay dosing until the parameters above have resolved.

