If a subject fails to dose the study drug within the 3 day window of the scheduled SC weekly dose during the blinded part of the study, they should contact the study site for instructions on dosing. The investigator and the Medical Monitor will determine if a late dose of study drug is acceptable to administer or if the dose should be skipped. If a subject misses >3 of the first 12 scheduled doses of study drug, the Gilead medical monitor should be contacted to discuss if the subject should be withdrawn from the study. See below for missed doses of concomitant medications (Section 5.4.1).

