- q Subjects not participating in the OLE will complete all week 12 assessments but will not receive an injection of study drug at the Week 12 visit. If subjects are eligible to participate in the OLE, then subjects complete all Week 12 assessments for the blinded period and then receive the first dose of the drug for OLE.
- r Study drug for 4 weekly doses will be dispensed at Weeks 1, 4 and 8
- s If not done in the prior 12 weeks. ECGs are to be performed supine
- t Per discretion of investigator

Study Visits: Open Label Extension														
Week	12	13	19	24	30	36	42	48	54	60	64	30 Day Follow Up	Unscheduled Visit ^k	ESDD
Window in Days	±3	±3	±5	±5	±5	±5	±5	±5	±5	±5	±5	±5		±3
Complete physical exam												X		
Targeted physical exam ^b		X	X	X	X	X	x	X	X	X	X	X	X	X
Vital signs and weight ^a		X	X	X	X	X	X	X	X	X	X	X	X	X
12 lead ECG											X		X ^k	
66 swollen and 68 tender joint count assessment				X		X		X		X	X	X	X ^k	X
Disease Specific Questionnaires and Activity Scales				X		X		X		X	X	X	X ^k	X
HAQ-DI				X		X		X		X	X	X	X ^k	X
SF-36				X		X		X		X	X	X	X ^k	X
Hematology ^c		X	X	X	X	X	X	X	X	X	X	X	X	X
Chemistry panel ^c		X	X	X	X	X	X	X	X	X	X	X	X ^k	X
Urinalysis		X	X	X	X	X	X	X	X	X	X	X		X
Erythrocyte Sedimentation Rate (ESR) Local lab			X	X	X	X	X	X	X	X	X	X		X
serum β-HCG Pregnancy Test ^d												X		X

Study Visits: Open Label Extension														
Week	12	13	19	24	30	36	42	48	54	60	64	30 Day Follow Up	Unscheduled Visit ^k	ESDD
Window in Days	±3	±3	±5	±5	±5	±5	±5	±5	±5	±5	±5	±5		±3
Urine Pregnancy test at study visits as marked – and every 4 weeks using kit at home (at weeks 16, 20, 28, 32, 40, 44, 52, and 56) ^d				X		X		X		X	X		X	
PK collection ^e				X							X			X
GS-5745 ADA collection ^f			X								X	X		
Biomarker collection	X			X		X		X		X				
C-Reactive Protein (hsCRP)		X	X	X	X	X	X	X	X	X	X	X	X	X
QuantiFERON-GOLD (QFT)									X					X
Chest x-ray (based on local TB screening guidelines)									X					
Estimated Glomerular Filtration Rate (based on MDRD study equation) performed at central lab				X		X		X		X				X

Study Visits: Open Label Extension														
Week	12	13	19	24	30	36	42	48	54	60	64	30 Day Follow Up	Unscheduled Visit ^k	ESDD
Window in Days	±3	±3	±5	±5	±5	±5	±5	±5	±5	±5	±5	±5		±3
Study Drug Dispensing ^g	X		X	X	X	X	X	X	X	X	no			
Study Drug Administration ^h														
Concomitant medications ⁱ	X	X	X	X	X	X	X	X	X	X	X	X	X	
Adverse Events ⁱ	X	X	X	X	X	X	X	X	X	X	X	X	X	

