### 1.2. Study Design

[figure not shown]
This is a Phase 2, double-blind, placebo-controlled, randomized multi-center study evaluating the efficacy and safety of andecaliximab as add-on therapy in subjects with moderately to severely active RA who have had an inadequate response to anti-TNF biologic therapy.

Subjects will be stratified by Disease Activity Score for 28 joints using the C-reactive protein (CRP) (DAS28[CRP]), either DAS28(CRP) > 5.1 or DAS28(CRP) > 3.2 and  $\leq$  5.1. In addition, subjects will be stratified by the prior number of RA biologics used (< 3 or  $\geq$  3).

Subjects will receive subcutaneous (SC) injections of study drug (andecaliximab or placebo) once a week for 12 weeks in the blinded period. Eligible subjects who complete the blinded period of the study may participate in the optional open-label extension (OLE), where they will receive weekly SC injections of 300 mg of andecaliximab for 52 weeks, in addition to continuing their current TNF inhibitor and MTX.

A total of approximately 75 subjects will be randomized in this study. The study design is shown in Figure 1-1.

**Figure 1-1.** Study Schema

Following completion of screening assessments, eligible subjects will be randomized in a blinded fashion in a 1:1:1 ratio as follows:

- **Group 1:** andecaliximab 300 mg (2 x 1 mL andecaliximab [150 mg/ml] SC injections) administered weekly (N=25)
- **Group 2:** andecaliximab 150 mg (1 x 1 mL andecaliximab [150 mg/ml] + Placebo-to-match 1 x 1 mL SC injection administered weekly (N=25)
- **Group 3:** Placebo-to-match (2 x 1 ml SC injections) administered weekly (N=25)

At the Week 12 visit, eligible subjects who choose to participate in the OLE will start weekly, open-label (OL), SC injections of 300 mg of andecaliximab for 52 weeks, in addition to their current SC administration of a TNF inhibitor and continued MTX.

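### The Week 12 (Day 85) row of the exposure table is out of reach for an on-schedule blinded completer who takes no open-label dose, because the 12-dose course ends on Day 78

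*SAP*

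**What the plan says.** **Exposure measure.** SAP 4.2.1 defines duration as "last dose date of any study drug - first dose date of any study drug + 1", taken "regardless of any temporary interruptions in study drug administration". No dosing interval is added after the last injection. Besides descriptive statistics, it plans cumulative counts of subjects exposed through Day 1, Day 8, Day 29, and then "Week 8 (Day 57), and Week 12 (Day 85". The summary is by treatment group in the Safety Analysis Set. If the last dose date is missing, the latest on-treatment date among several sources, including clinic visits, is used instead.

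**Blinded course.** Protocol 3.4: "Subjects will receive 12 SC injections of weekly study drug (GS-5745 or placebo) in the blinded period". Protocol 5.3 says that study drug "will be administered SC at the research center at Day 1 and Weeks 1, 4 and 8 during the blinded part of the study", and gives instructions for a subject who does not dose "within the 3 day window of the scheduled SC weekly dose during the blinded part of the study". Protocol Appendix 2 (blinded period, footnote q) says that subjects who do not enter the open-label extension (OLE) "will not receive an injection of study drug at the Week 12 visit".

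**Week 12 dose.** SAP 1.2: "At the Week 12 visit, eligible subjects who choose to participate in the OLE will start weekly, open-label (OL), SC injections of 300 mg". An injection at Week 12 is therefore the first open-label dose.

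**Period and grouping.** SAP 3.8.1 cuts data at the first open-label dose, but only for outputs that are based on study period. SAP 4.2.1 does not say that it is one of these. SAP 3.2 moves a subject from the randomised to the actual treatment group only if the two differ throughout treatment.

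**The concern.** The exposure rows reuse the nominal visit days of SAP Table 3-1. For the first four rows this works, because each of those days is also an on-site blinded dosing day. Day 85 is a visit day but not a blinded dosing day. Because the formula runs on dose dates, a subject who takes all 12 blinded injections on time and then stops does not qualify for the last row. That subject is last counted at Week 8, alongside someone who stopped on Day 57.

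What the row does show depends on a choice that the SAP leaves open:

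- **Open-label doses count**, as the words on any study drug suggest. The row then mainly counts OLE entrants. Under SAP 3.2, a placebo subject who enters the OLE stays in the placebo column, so open-label andecaliximab time is reported there.
- **The 3.8.1 cut applies.** The row is then nearly empty.

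On neither reading does it show who was exposed through the blinded course. Since SAP 4.2.2 drops the adherence summary, 4.2.1 is the only planned summary of how long subjects were dosed.

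**Working it through.** **Inputs**
- Duration = last dose date − first dose date + 1 (SAP 4.2.1); the first dose is on Study Day 1 (SAP 3.8.1)
- Rows at Days 1, 8, 29, 57 and 85 (SAP 4.2.1)
- 12 weekly blinded doses and up to 53 weekly OLE doses (Protocol 3.4)
- No Week 12 injection outside the OLE (Protocol Appendix 2, footnote q)
- 3-day dosing window (Protocol 5.3); I read it as ±3 days, which is an assumption

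**1. Reproduce the plan's days.** Visit day = 7 × week + 1. Weeks 1, 4, 8 and 12 give Days 8, 29, 57 and 85, exactly the SAP rows.

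**2. Place the doses.** Dose k is due on Day 1 + 7 × (k − 1).

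| Dose | Due | Exposure row on that day |
|---|---|---|
| 1 | Day 1 | Baseline |
| 2 | Day 8 | Week 1 |
| 5 | Day 29 | Week 4 |
| 9 | Day 57 | Week 8 |
| 12 (last blinded) | Day 78 | none |
| 13 (first open-label) | Day 85 | Week 12 |

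Two checks agree. Weeks 12 to 64 inclusive give 64 − 12 + 1 = 53 doses, the OLE maximum in Protocol 3.4, so the Week 12 dose belongs to the OLE. The 4 weekly doses dispensed at Week 8 (Appendix 2, footnote r) cover Weeks 8 to 11, ending with dose 12.

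**3. Duration for a completer with no open-label dose**
- On schedule: 78 − 1 + 1 = 78 days = 11.1 weeks; 85 − 78 = 7 days short
- Dose 12 three days late: 81 days = 11.6 weeks; 85 − 81 = 4 days short
- Dose 12 three days early: 75 days = 10.7 weeks; 85 − 75 = 10 days short
- If the week after dose 12 were counted: 78 + 6 = 84 days = 12.0 weeks; still 1 day short
- Dose 12 reaches Day 85 only if it is 85 − 78 = 7 or more days late

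**4. Duration if open-label doses count**
- One open-label dose on Day 85: 85 days = 12.1 weeks, of which 1 day is open-label
- Last dose at Week 13 (Day 92): 92 days = 13.1 weeks, of which 92 − 85 + 1 = 8 days are open-label
- The Week 12 visit window is ±3 days (Appendix 2). A subject whose only open-label dose falls on Days 82 to 84 has 82 to 84 days and also misses the row, so the row tracks OLE entry only approximately.

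**5. Reachable cut-offs with a ±3-day window.** Dose 11 falls on Days 68 to 74 and dose 12 on Days 75 to 81. The earliest in-window days for doses 2, 5, 9 and 12 are 8 − 3 = 5, 29 − 3 = 26, 57 − 3 = 54 and 78 − 3 = 75.

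**The case against.** **The last-dose record cannot be inspected.** SAP 3.8.1 takes the last dose date from the administration record flagged as permanent withdrawal. The case report form is not in the documents. It is unknown whether the end date is the injection date, whether the flag is set for someone who simply finishes 12 doses, or whether both periods share one form. If completers carried no flag, their dates might be treated as missing, and imputation could reach the Week 12 visit. This stands as a limit: how often imputation applies cannot be judged. It does not rescue the row, because a completer would then be counted only when the true dose date is absent.

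**The table may be meant as double-blind only.** All rows stop at Week 12 and match the double-blind windows of Table 3-1, so the 3.8.1 cut is a natural reading. That is fair. A reader might infer that open-label andecaliximab will be reported as placebo exposure; the documents do not settle this, since it follows only from the literal reading. The alternative reading leaves the row nearly empty, so it is defective either way.

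**The open-label amount may be small.** A reader might assume up to 365 open-label days per subject (Week 64 is Day 1 + 7 × 64 = 449; 449 − 85 + 1 = 365). That is the protocol maximum and not a figure for this study, which stopped after 15 enrolled subjects. The only open-label window in SAP Table 3-2 is OL Week 1, though it is open-ended.

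**The facts are recoverable elsewhere.** Duration statistics would show 11.1 weeks, completion of study drug is tabulated (SAP 4.1), and administrations are listed by subject (SAP 4.2.2). This stands, and it keeps the point minor.

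**Conclusion.** The point holds and is minor. On the SAP's own formula, a compliant completer without open-label dosing has 78 days of exposure, 7 days short of the last row, and no timing of dose 12 within the 3-day window closes the gap. The two exceptions are a dose 12 given 7 or more days late by agreement and a missing last-dose date imputed from a later visit. The Week 12 count is therefore either mainly a count of OLE entrants or close to zero.

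The effect is confined to the descriptive exposure table. The documents give neither the number of OLE entrants nor the split of the 15 subjects. If they split evenly, each arm would have 15 / 3 = 5 subjects, and one misplaced subject would move a percentage by 1 / 5 = 20 points.

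The conclusion rests on the nominal weekly schedule and on recorded dates being injection dates. A reader might go further and infer that safety or efficacy results are distorted. The documents do not support that: adverse events and laboratory abnormalities have their own period rules (SAP 7.1.6 and 7.2.2.2), and no efficacy summary uses exposure duration.

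**What to change.** 1. State in SAP 4.2.1 that the summary covers the double-blind period only.
2. Take the last blinded dose date as the last administration record before the first open-label dose, or the last record if there is none. Impute a missing date only from dates before the first open-label dose.
3. Replace the Week 12 (Day 85) row with Week 11 (nominal Day 78). Label it as duration and not as receipt of 12 doses, because the formula ignores interruptions.
4. If a dosing-window tolerance is used, apply the same one to every row after Day 1, for example at least 5, 26, 54 and 75 days, and footnote that the 3-day window is read as ±3 days. A tolerance on the last row alone would be inconsistent: a subject whose final dose is dose 2, 5 or 9, given early but in window, would miss the corresponding unadjusted row.
5. Report any open-label exposure separately as andecaliximab 300 mg by original arm, in a listing or one extra line.

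The cost is a few sentences of SAP text, one derived date and small table changes. No new data are needed, since study drug administration is already to be listed by subject. One limit remains: the 75-day cut separates dose 11 from dose 12 only inside the assumed window, because Protocol 5.3 lets later doses be accepted case by case.

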##### **3.1.2. Full Analysis Set**

The Full Analysis Set (FAS) includes all randomized subjects who received at least 1 dose of study drug. The study drug in this study is andecaliximab and placebo-to-match for andecaliximab. This is the primary analysis set for efficacy analyses.

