### **3.2. Subject Grouping**

For analyses based on the All Randomized Analysis Set, FAS, subjects will be grouped according to the treatment to which they were randomized. For analyses based on the Safety Analysis Set, subjects will be grouped according to actual treatment received. The actual treatment received will differ from the randomized treatment only when their actual treatment differs from randomized treatment for the entire treatment duration.

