### **3.8. Analysis Visit Windows**

#### **3.8.1. Definition of Study Day**

Study Day 1 is defined as the first dose date of study drug administration. The last dose date for the study drug will be the end date on study drug administration CRF for the record where the “study drug was permanently withdrawn” flag is “Yes”.

Study Day will be calculated from the Study Day 1 and derived as follows:

- For postdose study days: Assessment Date – Study Day 1 + 1
- For days prior to the first dose: Assessment Date – Study Day 1

For the outputs based on the study period (double-blind and OLE), the following rule will be applied:

- If subject continues into the OLE then the double-blind (DB) period reports will include the data collected prior to the date of the first dose of study drug in the OLE. The OLE summaries will include the data from the date of the first dose of OL treatment, inclusive.
- If subject does not continue into the OLE then all data collected starting from Day 1 will be included in the DB period summaries.

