#### 7.1.6. Summaries of Adverse Events and Deaths

Treatment-emergent AEs will be summarized based on the Safety Analysis Set.

The AEs will be reported by the treatment period. If subject does not continue into the OLE then all TEAEs will be reported in the DB treatment period (Day 1 to Week 12) summaries. For subjects who continue into the OLE, TEAEs during the DB treatment period are the AEs that started prior to the first dose of OL treatment. The AEs with the onset date on or after the first dose of the OL treatment and no later than 30 days after permanent discontinuation of study drug will be reported in the OLE summaries.

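### SAP 4.2.1 puts no period limit on exposure, so open-label 300 mg time enters the placebo and 150 mg arms' exposure statistics

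*SAP*

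**What the plan says.** SAP 4.2.1 defines total exposure as "last dose date of any study drug - first dose date of any study drug + 1), regardless of any temporary interruptions". It gives descriptive statistics and cumulative counts of subjects exposed through Days 1, 8, 29, 57 and 85, and adds: "Summaries will be provided by treatment group for the Safety Analysis Set". No study period is named.

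Other provisions settle what this means for a subject who enters the OLE:

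- SAP 1.2: "eligible subjects who choose to participate in the OLE will start weekly, open-label (OL), SC injections of 300 mg of andecaliximab for 52 weeks". Protocol 3.3.1 opens the OLE to all three randomised groups.
- SAP 3.1.2: "The study drug in this study is andecaliximab and placebo-to-match for andecaliximab". Open-label andecaliximab is therefore study drug.
- SAP 3.8.1: "The last dose date for the study drug will be the end date on study drug administration CRF for the record where the" flag for permanent withdrawal is set to yes. For a subject who continued into the OLE, that would be an open-label record.
- SAP 3.2, for the Safety Analysis Set: "The actual treatment received will differ from the randomized treatment only when their actual treatment differs from randomized treatment for the entire treatment duration". A subject on placebo for 12 weeks and then on open-label drug does not meet that condition and stays in the placebo group.

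Other outputs are split. SAP 7.1.6 says "The AEs will be reported by the treatment period", and SAP 7.2.2.2 does the same for laboratory abnormalities. The disposition table in SAP 4.1 lists "Did not complete study drug with reasons for premature discontinuation of study drug", also without a period.

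**The concern.** An exposure table tells the reader how long each arm was on its assigned treatment, and so gives the adverse event tables beside it their context. Here the adverse events of the placebo arm stop at the first open-label dose, but the arm's exposure runs on through open-label andecaliximab. For the 150 mg arm the added time is at a different dose. For the 300 mg arm the dose does not change, but blinded and open-label time are still mixed. With no testing planned, descriptive safety tables are a main product of the synoptic report, so an exposure column that does not match its label is worth correcting.

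**Working it through.** **Inputs.** There are 12 weekly blinded injections and up to 53 weekly OLE doses (Protocol 3.4). A subject not entering the OLE gets no injection at Week 12 (Protocol Appendix 2, blinded-period footnotes). The duration formula and time points are in SAP 4.2.1, and 15 subjects were enrolled (SAP 1.3). The documents do not give the number who entered the OLE or their number of open-label doses.

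**Reproducing the plan's calendar.** Day = 7 × week + 1 gives Days 8, 29, 57 and 85 for Weeks 1, 4, 8 and 12, as in SAP 4.2.1. Weekly dosing from Week 12 to Week 64 inclusive is 64 − 12 + 1 = 53 doses, as in Protocol 3.4.

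**Blinded exposure on schedule.** Dose k falls on Day 1 + 7(k − 1), so dose 12 is on Day 78. Duration = 78 − 1 + 1 = 78 days; 78/7 = 11.1 weeks.

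**Literal duration for a subject who enters the OLE.** The first open-label dose is on Day 85 and the second on Day 92.

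| Open-label doses | Last dose | Literal duration (weeks) | Blinded only (weeks) | Excess (weeks) |
|---|---|---|---|---|
| 0 | Day 78 | 11.1 | 11.1 | 0 |
| 1 | Day 85 | 85/7 = 12.1 | 11.1 | 1.0 |
| 2 | Day 92 | 92/7 = 13.1 | 11.1 | 2.0 |

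With two doses, open-label exposure by the same formula is 92 − 85 + 1 = 8 days = 1.1 weeks. The rest of the excess is the six days between Day 78 and Day 85.

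**Effect on an arm mean.** Assume 15/3 = 5 subjects per arm, all completing blinded dosing. Each subject with two open-label doses adds 2.0/5 = 0.4 weeks. The arm mean runs from 11.1 weeks if none enter the OLE to 13.1 if all five do.

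**Effect on the time-point counts.** I take exposed through a given day to mean a duration of at least that many days. Open-label dosing starts nominally on Day 85, so counts through Days 1, 8, 29 and 57 are the same under either reading. At Day 85 the last scheduled blinded dose falls short: Day 78, or Day 81 if three days late. On schedule, only a subject given open-label 300 mg reaches that row. The exceptions would be a later blinded dose agreed under Protocol 5.3 or an imputed last dose date. Each OLE entrant in an assumed arm of five therefore adds 20 percentage points to the Week 12 row.

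**The case against.** The best defence is that a double-blind table was intended. The time points stop at Week 12, which would be odd for a table covering a 52-week extension. SAP 3.8.1 also limits double-blind reports to data before the first open-label dose. This makes the intent plausible but does not repair the text. The rule in 3.8.1 applies to outputs based on the study period, and 4.2.1 is not identified as one. The formula and descriptive statistics have no cap. Under a double-blind reading the Day 85 row would be close to empty by construction, so that row needs attention either way.

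Other parts of the defence stand. SAP 4.2.2 provides a by-subject listing of study drug administration, from which the two periods can be separated by hand for 15 subjects. Three stronger readings are also tempting, and the documents do not support them:

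- **Very large inflation.** A reader might infer placebo durations of up to 449/7 = 64.1 weeks (last OLE dose at Week 64). That is only the formula's ceiling. The study was terminated after 15 subjects had enrolled, and the only open-label laboratory window in SAP Table 3-2 is OL Week 1, although Protocol Appendix 2 schedules tests at Weeks 19, 24 and later. That window is open-ended, so it suggests little open-label data without proving it.
- **Biased adverse event rates.** A reader might infer that blinded event counts are divided by an inflated denominator. SAP 7.1.6.1 counts each subject once per summary; no exposure-adjusted rate is planned.
- **Misattributed discontinuations.** A reader might infer that a placebo subject who finishes Week 12 and later stops open-label drug is tabulated as a placebo non-completer. SAP 4.1 does not define completion of study drug, so this is possible but not established.

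**Conclusion.** The point holds: SAP 4.2.1 is wrong as written, at low severity. Together with SAP 3.2 it places any open-label 300 mg time of placebo and 150 mg subjects in those arms' exposure statistics, while the event tables are split by period. The error is confined to the descriptive statistics and the Week 12 count. Its size is probably modest: 2.0 weeks for each subject with two open-label doses, or 0.4 weeks on a five-subject mean. Those figures assume on-schedule dosing, all 12 blinded doses taken, and equal arms of five. The actual size depends on OLE numbers that the documents do not give, and it is zero in any arm from which nobody entered the OLE. No hypothesis test, efficacy result or event rate depends on it.

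**What to change.** In SAP 4.2.1, replace the single duration with two:

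- Double-blind exposure = last blinded dose date − first blinded dose date + 1, summarised by blinded arm.
- OLE exposure = last open-label dose date − first open-label dose date + 1, summarised as open-label 300 mg by prior arm.

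In the double-blind table, align the Day 85 category with the last scheduled blinded dose (Day 78), so that a subject who completes blinded dosing on schedule can reach it. As a secondary clarification, state in SAP 4.1 whether completion of study drug, and the reasons for stopping, refer to the double-blind or the OLE period.

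The cost is a few lines of text and an extra block of columns in the exposure table, using dosing dates already collected. If the SAP is already final, SAP 1 provides for documenting the change in the clinical study report.
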